4 SELECTION AND EXCLUSION OF PEOPLE FROM THE RESEARCH

4.1 Inclusion Criteria

Any patient requiring GORE® EXCLUDER stenting® for the treatment of an unruptured Infra-renal Abdominal Aortic Aneurysm.

4.2 Non-inclusion Criteria

Patients whose clinical follow-up is not possible i.e., patients unable to return for monitoring visits (e.g., patients living abroad).

4.3 Explanation of the Endoprosthesis

Any patient for whom the GORE® EXCLUDER Endoprosthesis® has been withdrawn will be monitored for up to 5 years.

A minimum of one clinical follow-up will be carried out.

4.4 Premature discontinuation of the research for the patient

The following cases will be considered premature discontinuation of the study:

- Patient withdrawing his non-opposition
- Death
- Failure to Return

A patient who does not show up at the scheduled visit will be considered **temporarily** as having failed to return if the Investigator does not get any information about the patient:

- after having tried to contact him by phone several times (at least two documented phone calls)
- and after having sent him an invitation letter without any reply for 1 month.

All contact attempts will be documented.

If the Investigator obtains news about a temporarily-failed-to-return patient before the end of the study, that patient will no longer be considered failed-to-return; otherwise, he will be permanently categorized as having failed to return at the end of the study.

4.5 Procedures put in place to avoid failure-to-return

Several measures will be taken to avoid failure-to-return.

The study documents handed over to investigators during study set up highlight the fundamental importance of patient follow-up and data collection during the entire study.

The investigator will seek the means to contact the attending physician or the nearest trusted relation.

In the event of absence from a visit, the center investigator will contact him by phone several times (at least two documented calls) and send him an invitation letter. In the absence of a response, the attending physician will be contacted in a bid to obtain information on the patient's status and on all the elements needed to trace a possible clinical event related to the endoprosthesis (hospitalization, etc.).

In the absence of results from the procedures below, the patient living/deceased status will be documented by investigation in the municipality of birth by the Investigator.

5 TREATMENT ADMINISTERED TO RESEARCH SUBJECTS

5.1 Drugs authorized and prohibited under the Protocol including rescue medication

No medications are prohibited. Medications are used under usual conditions of surgery. The study does not involve any restriction or recommendation.

5.2 The medical device used

The device is the GORE® EXCLUDER Endoprosthesis® detailed in paragraph 1.1.4

A copy of the instructions for use supplied with each device is found in the investigator's file (Appendix 5).

5.3 Scientific Committee

A Scientific Committee common to all manufacturers has been established (Appendix 6). This multidisciplinary and independent Scientific Committee is composed of one methodologist and six practitioners (Cardiac Surgeon, Vascular Surgeon, Interventional Radiologist). This committee is the guarantor of scientific and methodological validity of the Protocol.

6. STATISTICAL ANALYSIS

6.2 *Strategy for analyzing collected data*

6.2.1 Patient characteristics and follow-up

Patient demographic and medical data and descriptive follow-up data will be described on the patient population included. Qualitative parameters will be described by their distribution frequency and bilateral confidence intervals associated at 95%, quantitative parameters by their average, minimum, maximum, median and quartiles standard deviation, number of missing values.

6.2.2 Criteria Studied

Main analyses:

The criteria studied are as follows:

- Death from all causes
- Aneurysm-related death
- Evolution of the diameter of the aneurysm.
- Types I, II and III endoleaks
- Migration
- Surgical conversion
- Re-intervention related to the initial procedure

Definitions :

- Death related to the aneurysm shall be defined as any death occurring as a result of a ruptured Abdominal Aortic Aneurysm or following any procedure intended to treat Abdominal Aortic Aneurysm.
If the death occurred within 30 days of any procedure intended to treat Abdominal Aortic Aneurysm, then it will be considered as related to the aneurysm unless proven otherwise. Deaths occurring beyond 30 days of any procedure intended to treat Abdominal Aortic Aneurysm and that are related to the procedure should be considered as related to the aneurysm.
- Distal migration is defined by a distal displacement strictly greater than 10mm. Proximal migration is defined either by proximal displacement strictly greater than 10mm, or by proximal displacement which covers one of the renal arteries; the reference examination being the first postoperative CT performed.

- An increase in the diameter of the aneurysm is defined by an increase strictly greater than 5 mm of maximum diameter of the highest measurable diameter of the aneurysm; the reference diameter being the diameter of the first post-operative check-up.

Each of the rates that match the Study criteria will be analyzed by calculating frequency distributions and bilateral confidence intervals of 95% (IC95) associated.

Event rates over time are described by survival curve according to the Kaplan-Meier method and the related Kaplan-Meier estimators will be calculated.

Additional Analyses:

All the analyzes may be stratified by center if recruitment in each center participating in the study is sufficient for such analyzes to be of interest. However, it must be emphasized that this Protocol in no way aims to compare the centers.

For exploratory purposes, the study criteria will also be analyzed depending on patient baseline characteristics:

- Age (in categories)
- Gender
- Diameter of Abdominal Aortic Aneurysm
- Patient status (normal or high surgical risk according to the Afssaps criteria, Appendices 3 and 4)

6.3 Statistical criteria for discontinuing the research

No discontinuation criterion

6.4 Method of management of missing, unused or invalid data

Missing data will be listed and presented in a tabulated form.

Patients will be considered as censored at the date of the last observation.

6.5 Choice of persons to be included in the analyses

All the patients in the register will be considered in the analysis.

6.6 Data Analysis Manager and Working Software

The Manager of data analysis performed by W. L. Gore & Associates is: MedPass International.

All the analyses will be managed under the responsibility of [name] located at MedPass International, [name].

All the analyses will be managed with SAS software.

A detailed statistical analysis plan will be prepared by MedPass for W. L. Gore & Associates.

7 RIGHT OF ACCESS TO DATA AND SOURCE DOCUMENTS

Individuals with direct access in accordance with current legislative and regulatory provisions, notably articles L.1121-3 and R.5121-13 of the Public Health Code (for example, investigators, individuals responsible for quality control, and any individuals appointed to collaborate in trials) take all the necessary precautions with a view to ensuring the confidentiality of information relating to experimental drugs, trials, subjects involved in trials, particularly as regards their identity, and results obtained. Data collected by these people are then anonymized.

8 LOGISTICS AND QUALITY ASSURANCE

The research will be supervised according to the Manager's standard operating procedures. The conduct of the research in the investigation centers and management of the subjects will be done in accordance with the ethical and medical guidelines.

Transcribing data into the case report form

eCRF

The study data will be recorded by participating physicians (investigators) on a eCRF. Information provided in the study questionnaire should be a reflection of those in the patient record.

➤ Monitoring

In order to ensure data quality, a monitoring plan is put in place. Among other things, this plan details the frequency of site visits and the proportion of monitored data. It is expected that at least 10% of the data be verified.

Monitoring elements regarding the quality of filling eCRF are performed by a CRA.

Participating physicians may be contacted in case of absence of filling of data after inclusion of patients or date of scheduled visit.

➤ Data Management

Systematic coherence control procedures are set up and documented. Correction procedures are traced. For the study data, Queries are issued and sent to different centers for resolution.

➤ Quality Assurance Procedure

Quality control is carried out continuously during the various stages of error correction, according to the Manager's standard operating procedures.

9 LEGAL AND ETHICAL CONSIDERATIONS

In this research, W. L. Gore & Associates and/or MedPass International are the Managers and are responsible for regulatory tasks.

9.1 *CNIL [French Data Protection Agency] Declaration*

This research is subject to the law of January 6, 1978 relating to Data Protection, as amended. Before its actual commencement, the processing of data collected in research is subject to referral to the French Advisory Committee on Information Processing in Material Research in the Field of Health (**CCTIRS**), and then the French Data Protection Agency (**CNIL**).

9.2 *Information and Non-opposition Form*

When selecting the subject, the physician will verify the selection and non-selection criteria and will inform the subject of the Study principle and his/her role.

The investigating physician should inform the patient and answer all his/her questions.

The patient must be informed of his/her rights to be able to object to, if he/she so wishes, the analysis of data concerning them, before any action necessary to research.

In this context, an Information and Non-opposition Form is prepared.

This Information Form includes the data requested by Afssaps and HAS in Appendix II of the report dated July 7, 2009 (Appendix 2).

9.3 *Final report on the Research*

The final report on the research will be written by W. L. Gore & Associates. This report will be sent to each of the investigators.

10 DATA PROCESSING AND STORAGE OF DOCUMENTS AND DATA RELATING TO THE RESEARCH

Documents pertaining to research must be stored by all parties involved for a period of 15 years after the end of the research.

This indexed storage will comprise at least:

- Successive versions of the Protocol (identified by the version No. and date),
- The letters of correspondence with the Manager,
- A completed and validated case report form for each subject enrolled,
- All appendices specific to the study,
- The final report of the study.

The database from which the statistical analysis was drawn must also be stored by the Analysis Manager (paper or electronic medium).

11 RULES RELATING TO PUBLICATION

- W. L. Gore & Associates is the proprietor of all data, analysis and results relating to the GORE® EXCLUDER Endoprosthesis® and no use or transmission to a third party may be made without its prior consent.

However, the consultant is free to independently use and develop data from the medical records of his own patients and also data and information:

- that were known to the consultant prior to their disclosure by manufacturers;
- that are or become legally accessible to the public;
- that are released from confidentiality status by written agreement of the manufacturer.

Appendix 1: Opinion of HAS dated July 13, 2010

HAUTE AUTORITÉ DE SANTÉ
NATIONAL COMMISSION FOR EVALUATION OF MEDICAL DEVICES
AND HEALTH TECHNOLOGIES
OPINION OF THE COMMISSION

July 13, 2010

Devices : Abdominal Aortic Endoprosthesis (Title III - Chapter 1 - Section 1 - Subsection 2 - paragraph 4 of the list of products and services mentioned in Article L. 165-1 of the Social Security Code)

Pursuant to:

- Decree No. 2004-1419 of 23 December 2004 on the management of products and services mentioned in Article L. 165-13 of the Social Security Code authorizing the Evaluation of Products and Services Commission (CEPP), on its own initiative or at the request of Ministers in charge of Social Security, to reevaluate the expected or actual services of the products or services listed as provided for in Article L. 165-1 (Article 13 of the Decree);
- self-referral to CEPP dated April 5, 2006 relating, in particular, to post-registration study objectives required within the framework of the renewal of registration of Abdominal Aortic Endoprostheses listed under brand name;
- the proposals of the mandated Working Group;

the National Commission for Evaluation of Medical Devices and Health Technologies recommends amending the conditions for renewal of registration of Abdominal Aortic Endoprostheses, listed under the brand name, in the following manner.

Terms of Renewal

CNEDiMETS subjects the renewal of registration of each endoprosthesis to the presentation of results of a specific follow-up study implemented on a cohort of patients representative of the population treated in real life conditions.

The objective of each study is to evaluate the usefulness of the technique by documenting overall mortality, complications (endoleak, migration), the rate of surgical conversion, evolution and rupture of the aneurysm, in the long term, that is, beyond 5 years.

This prospective cohort study shall involve at least 150 patients implanted after registration on the LPPR [List of Reimbursable Products and Services].

The results of the follow-up study shall be forwarded to CNEDiMETS once a year, for consideration.

The evaluation of this follow-up may lead CNEDiMETS to recommend that reimbursement for the EPA concerned be maintained or suppressed.

APPENDIX 3: Normal surgical risk patient

Definition of normal surgical risk patient
eligible for abdominal aortic stenting

HAS Report dated July 7, 2009

The reassessment of the benefit-risk balance can help lift the high-risk patient restrictions. Endovascular treatment can be offered as first-line surgery for **normal surgical risk and favorable anatomic criteria patients** and after informing patients of the benefits and risks of both methods.

The treatment may be recommended for a normal surgical risk patient only if the following anatomical criteria are met:

- neck without thrombus or major circumferential calcification
- proximal neck with parallel edges > 15 mm
- angle of the proximal neck: - < 40°
- or between 40° and 60°, provided that the length of the neck is more than 20 mm

The diameter of the proximal neck, the state of the distal neck (iliac anchor point(s)), the iliofemoral accesses must be compatible with the implantation system and the endoprosthesis used.

It should be noted that the introduction of an EPA in a patient with normal surgical risk should not lead to the voluntary exclusion of functional visceral arteries including the hypogastric artery, apart from the inferior mesenteric artery.

APPENDIX 4: High surgical risk patient

Definition of high surgical risk patient

HAS Report dated July 7, 2009

Patients at high surgical risk must present one of the following factors:

- Age greater than or equal to 80 years.
- Coronary artery disease (history of myocardial infarction or angina) with positive functional testing and coronary lesions for which revascularization is impossible or not indicated.
- Cardiac failure with patent clinical manifestations.
- Inoperable aortic stenosis.
- LVEF < 40 %.
- Chronic respiratory failure objectified by one of the following criteria:
 - o FEV < 1.2 l/sec ;
 - o VC <50% of the predicted value according to age, sex and weight;
 - o Arterial blood gases in the absence of oxygen: PaCO²> 45 mm Hg or PaO² < 60 mm Hg;
 - o oxygen therapy at home.
- Renal impairment if creatinine > 200 µmol/l before injection of contrast medium.
- Hostile abdomen, including the presence of ascites or other signs of portal hypertension.

[REDACTED]

[REDACTED]

| [REDACTED]

| [REDACTED]

| [REDACTED]

| [REDACTED]

[REDACTED]

[figure not shown]
| [REDACTED]

[REDACTED]

| [REDACTED]

[REDACTED]

| [REDACTED]

# STATISTICAL ANALYSIS PLAN

[figure not shown]
Gore-excluder\_SAP\_V4.0

Sponsor : W.L. GORE

Device : GORE® EXCLUDER®

[figure not shown]
Protocol Nr: FPR AAA 12-02

Versions	Date	Documents used / comments
Version 3.1	26/11/2015	SAP V3.0 + SAR comments from WL Gore (25NOV2015) + update of WL Gore address + update of signature page + update of protocol version + update of number of sites involved
Version 3.0	25/11/2015	SAP V2.1 + SAR comments from WL Gore (19NOV2015) + Modification of Table 3, Table 4, Table 5 and Table 28 titles + Addition of listing "Implantation main indication" + change Listing 5: "Other abnormalities observed" into "Occlusion, stenosis and other abnormalities observed"
Version 2.1	27/10/2014	SAP V2.0 + Clarification of the SAF population definition + Listing 3 title modification
Version 2.0	13/10/2014	SAP V1.1 + update of AAA following CRF modification
Version 1.1	26/07/2013	SAP V1 + update of derived criteria calculation section + addition of statistical tables and listings
Version 1	12/04/2013	Protocol Number FPR AAA 12-02 (Version 5.1)

**STATISTICAL  
ANALYSIS PLAN**

Gore-excluder\_SAP\_V4.0.doc  
Sponsor : W.L. GORE  
Device : GORE® EXCLUDER®  
Protocol Nr: FPR AAA 12-02

# STATISTICAL ANALYSIS PLAN

FPR AAA 12-02

Page 4/17

**STATISTICAL ANALYSIS PLAN**

FPR AAA 12-02

**List of abbreviations and definition of terms**

AAA	Abdominal Aortic Aneurysms
AE	Adverse Event
FUP	Follow-up
ICU	Intensive Care Unit
ITT	Intent-To-Treat population
LPP	List of products
LPPR	List of products and refundable services
SAF	Safety population
SAP	Statistical Analysis Plan

# STATISTICAL ANALYSIS PLAN

## 1. OVERVIEW

This statistical analysis plan (SAP) describes the planned statistical analyses of the data collected in the course of the Register Gore® Excluder® AAA France.

This SAP provides additional details concerning the statistical analyses outlined in the protocol (version dated 29FEB2012). The purpose of the SAP is to ensure the credibility of the study findings by pre-specifying the statistical approaches to the analysis of study data.

### 1.1. Study Objective

The objective of this study is to assess the usefulness of the technique by documenting overall mortality, complications (endoleak, migration), the rate of surgical conversion, the evolution and rupture of the aneurysm, in the long term, that is, 5 years, on a cohort of patients representative of the population treated in real life conditions.

### 1.2. Study Design

The study is a observational, prospective and multicentric register of the GORE® EXCLUDER® AAA Endoprosthesis used to treat infrarenal abdominal aortic aneurysms in which 180 patients are enrolled from 29 sites and followed during 5 years minimum.

### 1.3. Study Plan

#### 1.3.1. Sample Size

A total of 180 patients are enrolled in this study, [REDACTED]

#### 1.3.2. Patient's Follow-up

8 visits are scheduled:

- Visit 1 : Baseline
- Visit 2 : Procedure
- Visit 3 : Discharge
- Visit 4 : Post operatory (or in the month following the surgery)
- Visit 5 : 6 months Follow-up
- Visit 6 : 1 year Follow-up
- Visit 7 : 2 years Follow-up
- Visit 8 : 3 years Follow-up
- Visit 9 : 4 years Follow-up
- Visit 10 : 5 years Follow-up

#### 1.3.3. Study Device

The studied device is the GORE® EXCLUDER® Endoprosthesis and any evolution registered on LPP.

# STATISTICAL ANALYSIS PLAN

## 1.3.4. Study Assessments

The following flowchart applies to the study:

	Post operative follow-up (D1 à D30)	Follow-up at 6 months	Follow-up at 1, 2, 3, 4 and 5 years	Intermediate follow-up***
Clinic exam	X	X	X	X
Abdominal X-ray without preparation under 3 angles (face, profile and 3/4)	X 	X*	X*	X*
Tomography with contrast product	X	X	X	X
MRI	X*	X*	X*	X*
Vascular echo-doppler	X**	X**	X**	X**

\* if tomography with contrast product cannot be performed

\*\* If MRI cannot be performed

\*\*\* Intermediate follow up are realized only if leak, deterioration of endoprosthesis or evolution of aneurysms are noticed in the last follow up. The follow-up needs to be done within 3 months after the exam which noticed the anomaly.

(1) Radiography in postoperative follow-up will not be necessary in case of 3D reconstruction performed during tomography.

## 2. STATISTICAL METHODS

### 2.1. General Statistical Considerations

#### 2.1.1. Time Points Definition

Baseline data is defined as the last available observation recorded before the first study device exposition for the patient.

Visit(n) data is defined as the last available observation on or before the Visit(n) time point following the first study device exposition for the patient.

Endpoint data is defined as the last follow-up at 5 years or, if the data is missing, as the last available observation recorded for the patient.

If the hospital discharge visit did not occur before the post-operative follow-up, it will be considered as an unscheduled visit.

#### 2.1.2. Derived Criteria Calculation

- Age classes will be the following:
  - Age < 80 years
  - Age ≥ 80 years
- Body Mass Index will be calculated as :  

$$\text{BMI} = \text{weight (kg)} / (\text{height (m)})^2$$
- Duration between two dates i and j will be calculated as:  

$$\text{Duration } i, j = \text{Date } j - \text{Date } i + 1$$
- If no clinical exam is done at a particular visit, the visit date will be the last imaging exam date reported for this visit.
- Total study duration will be calculated as:  

$$\text{Total study duration} = \text{study exit date} - \text{procedure date} + 1$$
 If the procedure date is not available, the baseline will be used instead.

# STATISTICAL ANALYSIS PLAN

- All deviations reported by the investigators will be listed.

## 2.4.2. Patient Characteristics

Descriptive statistics will be used to draw up a recapitulation of ITT patients characteristics at baseline and procedure.

### 2.4.2.1. Baseline

- Demographics
- Medical condition
- Surgical Risk
- Aneurysm characteristics

### 2.4.2.2. Procedure

- Implantation main indication (a listing will also be presented).
- Implantation parameters (all patients not implanted with GORE® EXCLUDER® AAA Endoprosthesis bifurcated will be listed)
- Procedure evaluation and results (a listing of all associated surgical/endovascular procedures details and a listing of all other abnormalities observed will be presented)
- GORE® EXCLUDER® AAA Endoprosthesis details (listing)
- Discharge: Stay in ICU

## 2.4.3. Endpoints Analyses

The endpoint analyses will be performed on the ITT population.

Primary analysis consists to study the 5-year mortality of patients who received the endoprosthesis. Secondary analyses consist to study the other safety parameters on patients who received the endoprosthesis.

The dates to be used for the “aneurysm diameter evolution” survival analysis will be the date of the imaging exam on which it has been reported. If it is missing, the corresponding “clinical exam” date will be used instead.

The same will be done for the “endoleak complication” and “device migration” survival analyses.

### 2.4.3.1. Primary Analysis

The 5-year mortality survival curve will be described according to the Kaplan-Meier method. The associated Kaplan-Meier estimators will be calculated. Only events occurring up to 5 years (1826 days) of follow-up will be analyzed for mortality survival curve.

### 2.4.3.2. Secondary Analyses

The surgical conversion rate during procedure and the corresponding 95% confidence interval will be provided.

The following parameters will be presented using the Kaplan-Meier survival curves:

- Mortality related to the aneurysm
- Aneurysm diameter evolution
- Endoleak complication, for each type (I, II and III)
- Device migration overall and by type (distal, proximal)
- Re-intervention

For the parameters “Aneurysm diameter evolution”, “Endoleak complication” and “Device migration”, the date to be used for the survival analysis is the date of the first visit where the parameter is reported. Only events occurring up to 5 years (1826 days) of follow-up will be analyzed for these survival curves.

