2 OBJECTIVE OF THE STUDY

The objective of this Study is to evaluate the usefulness of the technique by documenting:

- Overall mortality,
- Complications (endoleak, migration),
- The surgical conversion rate,
- The evolution and rupture of the aneurysm,

in the long term, that is, 5 years, on a cohort of patients representative of the population treated in real life conditions.

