3.3 Evaluation Criteria

These criteria are measured postoperatively or within one month after surgery, at 6 months, 12 months and then annually for 5 years, with an annual report issued to be submitted to the French National Authority for Health:

- Overall mortality rate,
- Mortality rate related to the aneurysm,
- Evolution of the diameter of the aneurysm
- Rate of Endoleaks for Type I, II and III
- Migration rate,
- Rate of surgical conversion,
- Rate of endovascular or surgical re-intervention.

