3.4 Evaluation Parameters

General Data

- Age
- Gender
- Diameter of Abdominal Aortic Aneurysm
- Patient status (normal or high surgical risk according to the Afssaps criteria, Appendices 3 and 4)
- All references and evolution of the range of the GORE® EXCLUDER Endoprosthesis®

Data related to the procedure (at all control times):

- Death from all causes
- Aneurysm-related death
- Evolution of the diameter of the aneurysm
- Types I, II and III endoleak
- Migration
- Surgical conversion
- Re-intervention related to the initial procedure

Definitions :

Death related to the aneurysm shall be defined as any death occurring as a result of a ruptured Abdominal Aortic Aneurysm or following any procedure intended to treat Abdominal Aortic Aneurysm.

If the death occurred within 30 days of any procedure intended to treat Abdominal Aortic Aneurysm, then it will be considered as related to the aneurysm unless proven otherwise. Deaths occurring beyond 30 days of any procedure intended to treat Abdominal Aortic Aneurysm and that are related to the procedure should be considered as related to the aneurysm.

Distal migration is defined by a distal displacement strictly greater than 10 mm. Proximal migration is defined either by proximal displacement strictly greater than 10 mm, or by proximal displacement which covers one of the renal arteries; the reference examination being the first postoperative CT performed.

An increased aneurysm diameter is defined as an increase strictly greater than 5 mm of the largest measurable diameter of the aneurysm; the reference diameter being the diameter of the first post-operative check-up.

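### The visible SAP reports surgical conversion only for the index procedure, although the objective and protocol call for a rate followed over 5 years

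*SAP*

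**What the plan says.** **Objective.** SAP 1.1 sets out to document "the rate of surgical conversion, the evolution and rupture of the aneurysm, in the long term, that is, 5 years". Protocol section 2 has the same objective and lists "The surgical conversion rate" as an item of its own.

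**Measurement.** Protocol 3.3 includes the rate of surgical conversion in its criteria and says: "These criteria are measured postoperatively or within one month after surgery, at 6 months, 12 months and then annually for 5 years". A separate line in the same list is "Rate of endovascular or surgical re-intervention". Protocol 3.4 places surgical conversion under "Data related to the procedure (at all control times").

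**Protocol analysis.** Section 6.2.2 lists surgical conversion among the main-analysis criteria. It asks for a frequency with a two-sided 95% confidence interval for each rate, and adds: "Event rates over time are described by survival curve according to the Kaplan-Meier method and the related Kaplan-Meier estimators will be calculated".

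**SAP analysis.** Section 2.4.3.2 says: "The surgical conversion rate during procedure and the corresponding 95% confidence interval will be provided". The Kaplan-Meier list that follows covers aneurysm-related mortality, diameter evolution, endoleak, migration and re-intervention, but not conversion. In SAP 5.1.2.2, conversion is Table 34, a Type 3 (frequency) table. Tables 35 to 44 are all Type 10 (survival).

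**The concern.** The SAP presents itself as adding detail to the protocol's analyses. On this outcome it narrows one instead, and the visible text gives no reason. A criterion followed for 5 years becomes a proportion fixed when the procedure ends.

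The conversion rate is one of the outcomes that the HAS opinion (Protocol 1.1.3 and Appendix 1) requires the follow-up study to document in the long term, and the evaluation of that study bears on reimbursement. No threshold is set for it. The title of Table 34 carries no procedural limit, so a reader of the report would take it as the study's conversion rate. Any conversion during follow-up would be missing from it.

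**Working it through.** The documents state no conversion rate and no precision target for one, so there is no plan figure to reproduce. The check is a comparison of texts, followed by an illustration of size.

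**Step 1: time window**

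| Source | Window for conversion |
|---|---|
| Protocol 2, SAP 1.1 | Long term, 5 years |
| Protocol 3.3 | Postoperative, 6 and 12 months, then yearly to 5 years |
| Protocol 3.4, read with the 3.2 schedule | Every control visit |
| SAP 2.4.3.2 | The procedure only |

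An event that could occur only in the operating room would not need recording at every visit to 5 years. The SAP's own restriction to the procedure also implies that conversion can occur at other times. Protocol 4.3 adds that a patient whose endoprosthesis "has been withdrawn will be monitored for up to 5 years", though it does not say when the withdrawal takes place.

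**Step 2: method.** Protocol 6.2.2 sets two methods: a proportion with an interval for each rate, and Kaplan-Meier for event rates over time. The visible SAP applies only the first to conversion, and only to the procedure. It applies Kaplan-Meier, to 1826 days (5 × 365.25 = 1826.25), to every other listed secondary parameter.

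**Step 3: could another table supply the rate?** Re-intervention has a survival table (Table 44). Any late conversion counted there would be pooled with endovascular and other surgical re-interventions, so no conversion rate could be read from it. Protocol 3.3 lists the two as separate criteria. The visible text does not say whether a late conversion counts as a re-intervention.

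**Step 4: size, illustration only.** Input from the documents: n = 180 (Protocol 1.4). Assumed: 1 intra-operative conversion and k later ones. The crude total is (1 + k)/180, with a Clopper-Pearson 95% interval. It ignores censoring.

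| Later conversions k (assumed) | Total | Crude rate (95% CI) | Understatement by Table 34 (k/180) |
|---|---|---|---|
| 0 | 1/180 | 0.56% (0.01 to 3.06) | 0 points |
| 2 | 3/180 | 1.67% (0.35 to 4.79) | 1.11 points |
| 4 | 5/180 | 2.78% (0.91 to 6.36) | 2.22 points |
| 9 | 10/180 | 5.56% (2.70 to 9.98) | 5.00 points |

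In every row Table 34 would show 0.56% (0.01 to 3.06).

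To relate k to yearly hazards, the 5-year cumulative incidence of late conversion is h/(h + d) × (1 − exp(−5(h + d))), where h is the conversion hazard and d the death hazard, both assumed.

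| h per year | d = 0 | d = 7% per year |
|---|---|---|
| 0.2% | 1.0%, 1.8 patients | 0.8%, 1.5 patients |
| 0.5% | 2.5%, 4.4 patients | 2.1%, 3.8 patients |
| 1.0% | 4.9%, 8.8 patients | 4.1%, 7.4 patients |

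None of these patients would enter a rate limited to the procedure.

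**The case against.** **Text that cannot be seen.** The text following 2.4.3.2 and the entries after Table 44 are redacted, the listings are partly so, and SAP 2.1.3 to 2.4.1 is largely not shown. The contents list puts the safety section after 2.4.3, but it stops at third-level headings and would not reveal a further subsection of 2.4.3. A later conversion analysis, or a definition of conversion, could sit in any of these places. This stands as a limit on the claim, which concerns the visible text only. For the same reason, the absence of a definition can be asserted for the protocol's visible text but not for the SAP as a whole.

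**Kaplan-Meier is not assigned to conversion by name.** This is true, and 6.2.2 does not itself say 5 years. The horizon comes from the objective and from 3.3 and 3.4. The main gap is the time window, and a cumulative incidence to 5 years could also fill it. Kaplan-Meier is nevertheless the protocol's stated method for event rates over time.

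**Late events may appear under re-intervention.** They may, so the events themselves might not be lost. The separate conversion rate would be.

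**The outcome is secondary and descriptive.** The primary analysis, 5-year mortality, is unaffected, and no hypothesis or threshold depends on conversion. That limits the damage. It does not justify leaving an outcome named in the objective without its long-term analysis.

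**The counts are assumed.** They are, and nothing in the documents supports one row over another. The direction needs no assumption: leaving out later events cannot overstate the crude rate.

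**Conclusion.** The concern holds for the visible text and should be resolved before the analysis is run. Followed as written, SAP 2.4.3.2 and Table 34 give an intra-operative proportion where the objective and Protocol 3.3, 3.4 and 6.2.2 call for a rate over 5 years. The two agree only if no conversion follows the procedure. The understatement is zero in that case, and 1.1 to 5.0 percentage points for 2 to 9 later conversions in 180, all assumed counts. The conclusion rests on reading surgical conversion as an event that can occur during follow-up, as the protocol's visit schedule for it implies, and on the redacted or unseen SAP text not already holding the analysis.

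**What to change.** 1. In SAP 2.4.3.2, add to the Kaplan-Meier parameters: time to first surgical conversion, from the procedure to 1826 days, counting intra-operative conversions and those recorded at any control visit.
2. Report it in a new Type 10 table with a 95% confidence interval on the 5-year estimate. The layout in SAP 4.3.3 shows an interval only under the median, which a rare event will not reach.
3. Keep the procedural proportion and retitle Table 34 as intra-operative surgical conversion.
4. State the event date. The visible date rules in 2.4.3 and 2.4.3.2 cover only diameter, endoleak and migration. The date of the conversion operation, or failing that the date of the visit at which it is reported, would serve. Say also how death is handled, since censoring at death makes the curve a net risk.
5. Helpful but not essential: define surgical conversion, and say whether a late one also counts as a re-intervention in Table 44.
6. If unseen text already holds this analysis, cross-reference it from 2.4.3.2 and retitle Table 34.

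The cost is SAP wording and one more table. Protocol 3.4 already records conversion at all control times, so no new outcome has to be collected. Whether the case report form holds the operation date cannot be seen from these documents, hence the fallback to the visit date.
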